6.3.2 Product Shipment, Storage, and Accountability

6.3.2.1 Product Shipment

The investigational product, MenACYW conjugate vaccine (single-dose vials), and control product will be supplied by the Sponsor.

The Clinical Logistics Coordinator will contact the Investigator or a designee to determine the dates and times of delivery of products.

Each vaccine shipment will include a temperature-monitoring device to verify maintenance of the cold chain during transit. On delivery of the product to the site, the person in charge of product receipt will follow the instructions given in the Operating Guidelines, including checking that the cold chain was maintained during shipment (i.e., verification of the temperature recorders). If there is an indication that the cold chain was broken, this person should immediately quarantine the product, alert the Sanofi Pasteur representative, and request authorization from Sanofi Pasteur to use the product.

The concomitant products will be sourced locally by the Investigational sites.

6.3.2.2 Product Storage

The Investigator will be personally responsible for product management or will designate a staff member to assume this responsibility.

At the site, products must be kept in a secure place with restricted access. Vaccines will be stored in a refrigerator at a temperature ranging from +2°C to +8°C and should be protected from light. The vaccines must not be frozen.

For the investigational and control products, the temperature must be monitored and documented (see the Operating Guidelines) for the entire time that the vaccine is at the study site. In case of accidental freezing or disruption of the cold chain, vaccines must not be administered and must be

quarantined, and the Investigator or authorized designee should contact the Sanofi Pasteur representative for further instructions.

For concomitant products, the temperature will be monitored according to local standard practices.

6.3.2.3 Product Accountability

The person in charge of the investigational and control products management at the site will maintain records of product delivery to the study site, product inventory at the site, the dose(s) given to each subject, and the disposal of or return to the Sponsor of unused doses.

The necessary information on the product labels is to be entered into the source document and the CRB. If applicable, information may also be entered into the subject's vaccination card.

The Sponsor's monitoring staff will verify the study site's product accountability records against the record of administered doses in the CRBs and the communication from the IRT (if applicable).

In case of any expected or potential shortage of product during the study, the Investigator or an authorized designee should alert the Sanofi Pasteur representative as soon as possible, so that a shipment of extra doses can be arranged.

Concomitant products accountability will be managed according to local standard practices.

6.3.3 Replacement Doses

If a replacement dose of the investigational and/ or control product is required (e.g., because the syringe broke or particulate matter was observed in the syringe), the site personnel must either contact the IRT to receive the new dose allocation, or follow the instructions given in the Operating Guidelines.

6.3.4 Disposal of Unused Products

Unused or wasted investigational and control products will be returned to the Sponsor in accordance with the instructions in the Operating Guidelines. Product accountability will be verified throughout the study period.

6.3.5 Recall of Products

If the Sponsor makes a decision to launch a retrieval procedure, the Investigator(s) will be informed of what needs to be done.

6.4 Blinding and Code-breaking Procedures

Blinding and code-breaking procedures are not applicable to this study.

Given that the meningococcal vaccines (investigational and control) used in this study have different appearances, and individual group vaccination schedule differs in the number of vaccines administered and timing of their administration, the study has an open-label design. The laboratory personnel involved in testing the samples will be blinded.

6.5 Randomization and Allocation Procedures

On the day of Visit 1, subjects who meet the inclusion/exclusion criteria and whose parent / legally acceptable representative signs the ICF will be randomly assigned to Groups 1 through 3 in a 2:2:1 ratio, such that Group 1 will have approximately 320 subjects, Group 2 will have approximately 320 subjects, and Group 3 will have approximately 160 subjects.

Site staff will connect to the IRT system, enter the identification and security information, and confirm a minimal amount of data in response to IRT prompts. The IRT system will then provide the group assignment and subject number. The full detailed procedures for group allocation are described in the Operating Guidelines. If the subject is not eligible to participate in the study, then the information will only be recorded on the subject recruitment log.

Subject numbers that are assigned by the IRT system will consist of a 12-digit string (a 3-digit country identifier, a 4-digit study center identifier, and a 5-digit subject identifier). For example, Subject 826000100005 is the fifth subject enrolled in Center Number 1 in the UK (826 being the UK country code).

Subject numbers should not be reassigned for any reason. The randomization codes will be kept securely in the IRT system.

6.6 Treatment Compliance

The following measures will ensure that the vaccine doses administered comply with those planned, and that any non-compliance is documented so that it can be accounted for in the data analyses:

- All vaccinations will be administered by qualified study personnel
- The person in charge of product management at the site will maintain accountability records of product delivery to the study site, product inventory at the site, dose(s) given to each subject, and the disposal of unused or wasted doses

6.7 Concomitant Medications and Other Therapies

At the time of enrollment, ongoing medications including but not limited to other therapies (e.g., blood products), should be recorded in the source documents. All new medications prescribed for new medical conditions / AEs during study participation should also be recorded in the source documents.

Documentation in the CRB of concomitant medication(s) will be limited to specific categories of medication(s) (Categories 1, 2, and 3 as detailed below). Those will include Category 1, 2, and 3 medications ongoing at the time of inclusion in the study, or started at any time during the subject's participation in the trial. For category 3 medication, the period of reporting in CRB will be restricted to only 3 days (72 hours) prior to each blood sampling time point.

Collection period in source documents

Reportable medications (Category 1, 2, and 3) will be collected in the source documents from the day of first vaccination to the end of the trial.^a

Categories of Reportable medications and reporting period

Reportable medications include medications that impact or may impact the consistency of the safety information collected after any vaccination and/or the immune response to vaccination.

- Category 1: Reportable medications with potential impact on the evaluation of the safety of the study vaccines. For example, antipyretics, analgesics, non-steroidal anti-inflammatory drugs (NSAIDs), systemic corticosteroids (therapy duration less than 2 weeks), and other immune modulators. Category 1 medications do not define the Per-Protocol Analysis Set (PPAS).

Note: Topical steroids (Inhaled, otic, ophthalmic, nasal etc.) should not be captured or reported.

- Category 1 medications will be reported in the CRB from the day of first vaccination to the end of the solicited and unsolicited follow-up period after each vaccination. These medications will also be collected in the CRB for the 30-day period prior to the subsequent doses of the vaccine, wherever applicable (second, third, fourth, etc., in case of a multi-dose schedule with more than a 30-day interval between doses).
- Category 2: Reportable medications with potential impact on immune response of the study vaccines and used to define the PPAS. For example:
 - Flu vaccines administered within 14 days pre or post each trial vaccination, including the day of the study vaccination visit
 - Any vaccine other than study vaccines (vaccines non-described in the Protocol) within the 28 days (4 weeks) preceding or after the trial vaccination, including the day of the study vaccination visit.
 - Immune globulins, blood or blood-derived products: used in the 3 months preceding the first blood draw and up to the last blood draw
 - Immunosuppressive therapy such as immune-suppressors, immune-modulators with immunosuppressive properties, long-term systemic corticosteroids therapy (prednisone or equivalent for more than 2 consecutive weeks) within past 3 months, anti-cancer chemotherapy, anti-proliferative drugs such as DNA synthesis inhibitors, or radiation therapy: used in the 6 months preceding the first trial vaccination, and up to the last blood draw.
 - Category 2 medications will be reported in the CRB according to the collection period detailed above up to the last blood draw.

^a Subject's parents will be required to document all medications received in the Diary Cards. The sites will focus on only recording the medications belonging to the 3 categories in the other source documents.

- Category 3: Antibiotics that the subject received within 72 hours preceding each visit for blood draw related to IMP assessment (meningococcal vaccines) and used to define the PPAS.
 - Category 3 medications will be reported in the CRB for the period of 3 days (72 hours) before each blood draw.

Note: Topical antibiotics (Inhaled, otic, ophthalmic, nasal, etc.) should not be captured or reported.

The information reported in the CRB for each reported medication will be limited to:

- Trade name
- Rationale for the origin of prescription: Whether it was a prophylactic^a medication? Prophylactic medications will be recorded in the Action Taken section of the AE collection tables.
- Medication category (1, 2, or 3)
- Start and stop dates

Dosage and administration route, homeopathic medication, will not be recorded.

If the subject has received medications other than those listed in Categories 1, 2, and 3, the detailed information will be collected in the source documents only.

Medications given to treat an AE will be captured in the “Action Taken” section of the AE CRB only. No details will be recorded in the concomitant medication CRB unless the medication(s) received belongs to one of the prelisted categories.

7 Management of Samples

Blood samples for the assessment of antibody responses will be collected:

- Groups 1 and 2: 160 subjects in each group will be randomized to have 3 blood draws at the intervals mentioned below. The remaining subjects will only have 1 blood draw at Visit 5.
- Group 3: all subjects will have 3 blood draws.

For the subjects randomized to have 3 blood draws in Group 1 and Group 2, the first 2 blood draws will be performed in a staggered way – approximately half of the subjects (~70 subjects in each group) will have blood draws at Visit 2 and Visit 3 (subset A), and the remaining half (~90 subjects in each group) will have blood draws at Visit 3 and Visit 4 (subset B). The third blood draw will be performed at Visit 5 for all subjects.

Subset A (~70 subjects in each group):

- a pre-vaccination blood sample at Visit 2

^a Medication(s) prescribed for preventing AE occurrence (e.g. paracetamol to reduce the risk of fever)

- a blood sample at Visit 3 (30 days after vaccination at Visit 2)
- a blood sample at Visit 5 (30 days after vaccination at Visit 4)

Subset B (~90 subjects in each group):

- a blood sample at Visit 3 (30 days after vaccination at Visit 2)
- a pre-vaccination blood sample at Visit 4
- a blood sample at Visit 5 (30 days after vaccination at Visit 4)

For the subjects randomized to Group 3, the first 2 blood draws will be performed in a staggered way – approximately half of the subjects (~70 subjects) will have blood draws at Visit 2 and Visit 3 (subset A), and the remaining half (~90 subjects) will have blood draws at Visit 3 and Visit 4 (subset B). The third blood draw will be performed at Visit 5 for all subjects.

Subset A (~70 subjects):

- a pre-vaccination blood sample at Visit 2
- a blood sample at Visit 3 (30 days after vaccination at Visit 2)
- a blood sample at Visit 5 (30 days after vaccination at Visit 4)

Subset B (~90 subjects):

- a blood sample at Visit 3 (30 days after vaccination at Visit 2)
- a pre-vaccination blood sample at Visit 4
- a blood sample at Visit 5 (30 days after vaccination at Visit 4)

See the [Table of Study Procedures](#) and [Section 5.1.3](#) for details of the sampling schedule.

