The MET52 trial will support licensure of MenACYW conjugate vaccine in the EU. This is a Phase III study designed to evaluate the immunogenicity and describe the safety of MenACYW conjugate vaccine when administered concomitantly with a meningococcal serogroup B vaccine as part of a routine immunization program in healthy infants and toddlers. The UK was selected as the country in which the study will be conducted based on the national immunization program including a meningococcal serogroup B vaccine (Bexsero[®]). Bexsero[®] was licensed in Europe in 2013, and since July 2015 has been introduced into the UK's routine childhood immunization at 2, 4, and between 12 and 13 months of age (36).

2 Study Objectives

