5.1 Description of the Overall Study Design and Plan

5.1.1 Study Design

This study is a Phase III, open-label, randomized, parallel-group, active-controlled, multi-center study to evaluate the immunogenicity and describe the safety of MenACYW conjugate vaccine when administered concomitantly with a meningococcal group B vaccine (Bexsero[®]) and other routine pediatric vaccines as part of the National Immunization Schedule in healthy infants and toddlers in the UK.

Approximately 800 healthy infants aged ≥ 56 to ≤ 89 days (approximately 2 months of age) will be randomized 2:2:1 to the following 3 groups:

Group 1: MenACYW conjugate vaccine at 3 months and at 12 to 13 months of age; Bexsero[®] at 2, 4, and 12 to 13 months of age

Group 2: MenACYW conjugate vaccine at 3 months and at 12 to 13 months of age; Bexsero[®] at 2 and 4 months of age

Group 3: Bexsero[®] at 2, 4, and 12 to 13 months of age

Routine pediatric vaccines will be given to subjects in all groups according to the UK immunization schedule:

- Infanrix hexa[®] (Combined Diphtheria-Tetanus-acellular Pertussis [DTPa], Hepatitis B, Inactivated Poliovirus and *Haemophilus influenzae* type b Vaccine; DTPa-HBV-IPV+Hib) at 2, 3, and 4 months of age
- Rotarix[®] (rotavirus vaccine; RV) at 2 and 3 months of age
- Prevenar 13[®] (pneumococcal 13-valent conjugate vaccine; PCV13) at 2 and 4 months of age

The routine vaccines (Infanrix hexa[®], Rotarix[®], and Prevenar 13[®]) will be sourced by the investigators and administered as per the standard practices. MenACYW conjugate vaccine and Bexsero[®] will be provided by the Sponsor.

The routine pediatric vaccines administered in the second year of life (Menitorix[®], Priorix[®]/M-M-RVAXPRO[®], and PCV13 [for all groups], and Bexsero[®] [for Group 2]) may be given as per standard of care at the last study visit after completion of study procedures (Visit 5 at 13 to 14 months). For Group 2, Bexsero[®] will be provided by the Sponsor to complete the vaccination series for subjects enrolled in this group. Subjects in Group 3 will be offered a single dose of the licensed ACWY conjugate meningococcal vaccine (Nimenrix[®]). This is a non-study vaccine to be administered 30 days after the last study visit (Visit 5) at an additional optional visit, and will be outside the scope of the study evaluations. No immunogenicity and safety data will be collected after the administration of these vaccines.

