5.2.5 Exclusion Criteria

An individual fulfilling *any* of the following criteria is to be excluded from study enrollment:

- 1) Participation at the time of study enrollment (or in the 4 weeks preceding the first trial vaccination) or planned participation during the present trial period in another clinical trial investigating a vaccine, drug, medical device, or medical procedure
- 2) Receipt of any vaccine in the 4 weeks preceding the first trial vaccination (at Visit 1) or planned receipt of any vaccine in the 4 weeks before and/or following any trial vaccination except for influenza vaccination, which may be received at a gap of at least 2 weeks before or 2 weeks after any study vaccines. This exception includes monovalent pandemic influenza vaccines and multivalent influenza vaccines.
- 3) Previous vaccination against meningococcal disease with either the trial vaccine or another vaccine (i.e., mono- or polyvalent, polysaccharide, or conjugate meningococcal vaccine containing serogroups A, C, W, or Y; or meningococcal B serogroup-containing vaccine)
- 4) Previous vaccination (before Visit 1) with any pneumococcal, diphtheria, tetanus, pertussis, hepatitis B, Haemophilus influenzae type b (Hib), poliovirus, and/or rotavirus vaccines. Receipt of BCG vaccine at birth is acceptable.
- 5) Receipt of immune globulins, blood or blood-derived since birth
- 6) Known or suspected congenital or acquired immunodeficiency, including Severe Combined Immunodeficiency disorder (SCID); or receipt of immunosuppressive therapy, such as anti-cancer chemotherapy or radiation therapy; or long-term systemic corticosteroid therapy (prednisone or equivalent for more than 2 consecutive weeks) since birth

^a ≥ 56 to ≤ 89 days” means from the 56th day after birth to the day before the 90th day after birth

- 7) History of any neurologic disorders, including any seizures and progressive neurologic disorders or encephalopathy
- 8) History of *Neisseria meningitidis* infection, confirmed either clinically, serologically, or microbiologically
- 9) History of diphtheria, tetanus, pertussis, poliomyelitis, Hib, hepatitis B, *Streptococcus pneumoniae*, and/or rotavirus infection or disease
- 10) At high risk for meningococcal infection during the trial (specifically, but not limited to, subjects with persistent complement deficiency, with anatomic or functional asplenia, or subjects travelling to countries with high endemic or epidemic disease)

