12.2 Analysis Sets

All immunogenicity analyses will be performed on the PPAS. Additional immunogenicity analyses will be performed for exploratory purposes on the Full Analysis Set (FAS) according to the randomization group. All safety analyses will be performed on the Safety Analysis Set (SafAS).

The study vaccines refer to MenACYW conjugate vaccine, Bexsero[®] vaccine and concomitant routine vaccines in the pre-defined vaccination schedule from Visit 1 to Visit 4.

The investigational product only refers to MenACYW conjugate vaccine or Bexsero[®] vaccine.

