In addition to the reasons listed above, subjects will also be excluded from the PPAS2 if their serology sample did not produce a valid test result at Visit 4.

Vaccine correctness required by the PPAS2 includes not only the 1 dose of MenACYW conjugate vaccine for Group 1 and Group 2, and the 2 doses of Bexsero[®] for Groups 1 to 3, but also the concomitant routine vaccines as scheduled (Infanrix hexa[®], Rotarix[®], and Prevenar 13[®]) for Groups 1 to 3 during infant stage from Visit 1 to Visit 3.

In the event of a local or national immunization program with a pandemic influenza or coronavirus vaccine, subjects who receive 1 or more doses of a pandemic influenza or coronavirus vaccine, or the vaccine listed above at any time during the study will not be withdrawn from the study.

12.2.3.3 Per-Protocol Set for Second Year of Life Vaccination (12 to 13 Months of Age, PPAS3):

The PPAS3 is a subset of the FAS3.

During the second year of life, the immunogenicity analyses for meningococcal antigens (A, C, W and Y) are performed on serology obtained at Visit 5, which is 30 days after the administration of study vaccine(s) at Visit 4.

The subjects presenting with at least one of the following relevant protocol deviations will be excluded from the PPAS2:

- Subject did not meet all protocol-specified inclusion criteria or met at least one of the protocol-specified exclusion criteria
- Subject did not complete the vaccination schedule, including the infant schedule and the 12 to 13 months vaccination in second year of life, from Visit 1 to Visit 4
- Subject received a vaccine other than the one that he / she was randomized to receive during the infant stage or second year of life, from Visit 1 to Visit 4
- Preparation and / or administration of vaccine was not done as per-protocol during the infant stage or second year of life, from Visit 1 to Visit 4
- Subject did not receive vaccine in the proper time window during the second year of life:
 - Visit 4: 12 to 13 months of age
- Subject did not provide a post-dose serology sample in the proper time window or a post-dose serology sample was not drawn at Visit 5 in the second year of life:
 - Blood sampling 3 (Visit 5): Visit 4 + 30 days (+21 days)
- Subject received a protocol-prohibited therapy / medication / vaccine during the infant stage or second year of life prior to or at Visit 5

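### The vaccine rule behind the primary per-protocol set ends at day 28 and ignores antigen content, leaving three exposures between Visit 4 and the Visit 5 draw without an explicit exclusion

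*Protocol*

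**What the plan says.** **Entry.** Exclusion criterion 3 (section 5.2.5) bars any child with earlier meningococcal vaccination, including any "mono- or polyvalent, polysaccharide, or conjugate meningococcal vaccine containing serogroups A, C, W, or Y". It applies to vaccination before enrollment only.

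**After entry.** Section 6.7 introduces Category 2 as "Reportable medications with potential impact on immune response of the study vaccines and used to define the PPAS. For example". Its item on non-influenza vaccines reads "Any vaccine other than study vaccines (vaccines non-described in the Protocol) within the 28 days (4 weeks) preceding or after the trial vaccination". In the same list, the items on blood products and immunosuppressants run to the last blood draw.

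**Study vaccines.** Section 12.2 counts MenACYW, Bexsero and "concomitant routine vaccines in the pre-defined vaccination schedule from Visit 1 to Visit 4" as study vaccines.

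**PPAS3 (section 12.2.3.3).** This is the set for the primary comparison. Three of its exclusions matter here:
- a vaccine other than the one "randomized to receive during the infant stage or second year of life, from Visit 1 to Visit 4";
- a protocol-prohibited vaccine up to and including Visit 5, with no reference to Categories 2 and 3 (the PPAS1 and PPAS2 versions have that reference);
- other violations up to Visit 5 that affected the immune response, as decided by the clinical team before lock.

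**Timing.** The Visit 5 sample is due 30 days (+21) after Visit 4. The second-year routine vaccines, and Bexsero for Group 2, "may be given as per standard of care at the last study visit after completion of study procedures" (section 5.1.1). Section 1.4 says that Bexsero was "introduced into the UK's routine childhood immunization at 2, 4, and between 12 and 13 months of age".

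**The concern.** The primary contrast is MenACYW with Bexsero (Group 1) against MenACYW alone (Group 2), read from the Visit 5 titer. The vaccine rule is anchored to trial doses. It is anchored neither to that draw nor to whether the outside vaccine carries a measured antigen.

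Two kinds of exposure could pull the groups together and so favour non-inferiority. An outside dose containing A, C, W or Y can lift children in both groups over 1:8 whatever MenACYW did. Bexsero given to a Group 2 child before the draw erodes the comparator condition. The second is foreseeable: by the protocol's own account the national programme gives that dose at 12 to 13 months, while Group 2 waits until Visit 5 at 13 to 14 months.

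**Working it through.** **1. Windows.** The Visit 5 draw falls on day 30 to day 30 + 21 = 51 after Visit 4. The listed rule stops at day 28. For the latest permitted draw, days 29 to 51 are unlisted, which is 51 − 29 + 1 = 23 days.

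**2. Each exposure between Visit 4 and the draw, set against the stated rules.**

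| Exposure | Category 2 item | Wrong-vaccine criterion | What remains |
|---|---|---|---|
| (a) Outside A/C/W/Y vaccine, day 29 to draw | Past day 28 | Ends at Visit 4 | Undefined prohibited-vaccine criterion; judgement before lock |
| (b) Menitorix, MMR or PCV13, day 0 to 28 | Exempt on the literal parenthesis, since the protocol describes them | Ends at Visit 4 | The same |
| (c) Bexsero in Group 2 | Not reached: Bexsero is a study vaccine | Ends at Visit 4 | The same |

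On (b), section 5.2.7.1 sets a 4-week restriction around study vaccinations for vaccines other than the study vaccines. It exempts influenza vaccines but not vaccines that the protocol describes. The two sections therefore disagree.

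On (c), the vaccine-correctness sentence in section 12.2.3.3 makes matters worse. For Visit 4 it lists MenACYW alone for Group 1 and MenACYW plus Bexsero for Group 2, the reverse of section 5.1.1.

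**3. The plan's power.** The interval is the Wilson score interval for a difference, without continuity correction. Its lower limit is L = (p̂1 − p̂2) − √[(p̂1 − l1)² + (u2 − p̂2)²], where l1 and u2 are the single-group Wilson limits. Power is the exact binomial probability that L > −10%, with 224 per group and equal rates.

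| Serogroup | Rate | Stated | Recomputed |
|---|---|---|---|
| A | 92% | 95.9 | 96.6 |
| C | 90% | 92.5 | 93.3 |
| Y | 96% | 99.8 | 99.8 |
| W | 96% | 99.8 | 99.8 |
| Product | | 88.4 | 89.8 |

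The stated figures are reproduced to within 2 points.

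**4. Type I error if exposed children stay in.** Take serogroup C at the margin: 90% in Group 2 (the plan's rate) and 90 − 10 = 80% in Group 1. Let c be the exposed share. The documents give no value for c, so it is assumed.
- Outside serogroup C vaccine in both groups, every exposed child a responder: p′ = c + (1 − c)p.
- Early Bexsero in Group 2, exposed children responding as Group 1 does: p2′ = (1 − c) × 0.90 + c × 0.80.

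| c | Outside vaccine: rates | Type I error | Early Bexsero: rates | Type I error |
|---|---|---|---|---|
| 0 | 80.0 vs 90.0 | 2.5% | 80.0 vs 90.0 | 2.5% |
| 2% | 80.4 vs 90.2 | 2.9% | 80.0 vs 89.8 | 2.9% |
| 5% | 81.0 vs 90.5 | 3.6% | 80.0 vs 89.5 | 3.6% |
| 10% | 82.0 vs 91.0 | 4.9% | 80.0 vs 89.0 | 4.9% |

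**5. Power if they are excluded from both groups** (same method, product of four): 89.8% at 224 per group, 89.5% at 220 (c = 2%), 88.2% at 213 (5%) and 85.4% at 202 (10%).

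**The case against.** The strongest reply is that the protocol has more protection than the one Category 2 item, and most of that reply stands.

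- **The list is illustrative.** Category 2 is introduced by example, and an outside meningococcal vaccine fits its general description. This stands, but it leaves open which doses count.
- **Exposure before Visit 4.** A reader might infer that the months between Visit 3 and Visit 4 are unprotected. The documents do not support that: the wrong-vaccine criterion spans Visit 1 to Visit 4 and arguably reaches any outside vaccine in that interval. It also catches Bexsero given to Group 2 at or before Visit 4.
- **Exposure after Visit 4.** A reader might infer that contaminated titers necessarily remain in the primary analysis. That is not established either, because the prohibited-vaccine and other-violations criteria both run to Visit 5. But the first does not say what is prohibited, and the second presupposes a violation, whereas a dose after day 28 breaks no stated vaccine rule. Both leave room for decisions made where allocation is known. Section 6.7 also keeps medications outside the three categories in source documents only, so a dose judged not to be Category 2 may never reach the database under review.
- **Size.** A point difference that drifts inside −10 does not produce success. At 80.2% versus 90%, a difference of −9.8, the lower limit with 224 per group is about −16.4% and non-inferiority is declared for that serogroup only 2.9% of the time. All four serogroups must also pass. This stands, and it is why the effect is expressed here as type I error.
- **Left to the analysis plan.** Operational deviation lists often are. But here the protocol itself states a window and a scope, and both fit the primary endpoint poorly.

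**Conclusion.** The point holds as a defect in a stated rule: its window ends before the primary draw, its scope ignores antigen content, and its parenthesis conflicts with section 5.2.7.1. Three exposures between Visit 4 and the draw lack an explicit exclusion and depend on an undefined criterion or on open-label judgement.

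The direction of bias is towards non-inferiority. The size is modest at low rates: about 0.4 points of type I error at 2% exposure and 2.4 points at 10%. Those figures rest on assumed exposure rates, on full response in children given an outside vaccine, and on early-Bexsero children in Group 2 responding exactly as Group 1 does. A dose shortly before the draw may do less. The protocol does not state the composition of Menitorix, so its relevance to serogroup C is an assumption. The Bexsero gap does not depend on it.

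Because the rule defines the primary population, it should be settled before database lock.

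**What to change.** These changes concern the analysis set and data capture only.

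1. In section 6.7, delete the parenthesis on vaccines not described in the protocol, or reconcile it with section 5.2.7.1.
2. In section 12.2.3.3, name two PPAS3 exclusions: any vaccine containing serogroup A, C, W or Y other than the assigned MenACYW doses, from Visit 1 to the Visit 5 draw; and, in Group 2, any Bexsero dose from Visit 4 to that draw.
3. Record such doses in the case report book up to the Visit 5 draw.
4. Reconcile the vaccine-correctness sentence in section 12.2.3.3, in which Groups 1 and 2 are reversed, with section 5.1.1.

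The cost is protocol wording, a question about outside vaccines at the visits, one data-review check, and a few subjects leaving PPAS3. If 5% left both groups, overall power would fall from 89.8% to 88.2%.
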